Effects of a Cognitive Interference Task on Alcohol Craving and Consumption Among Women

NCT number NCT04924283
Document Date 02/15/2022

Effects of a Cognitive Interference Task on Alcohol Craving and Consumption among Women ([name], Assistant Professor, Dept. of Psychiatry)

Despite the prevalence and serious consequences of alcohol use disorder (AUD) among women, only 5.4% receive treatment.¹ Brief mobile interventions are a promising way to deliver accessible, evidence-based interventions to women who would not otherwise seek help. The primary objective of the proposed study is to test the effects of a brief, cognitive interference task (Tetris) in reducing alcohol craving and consumption among women with at-risk drinking according to NIAAA guidelines.³ Elaboration Intrusion Theory (EIT) proposes that visual working memory processes are central to craving, and that imagined experiences of engaging in substance use increases motivation to engage in the actual behavior.⁴ In laboratory and real-world settings, participants report decreased craving for food and substances after completing Tetris, a visuospatial task that increases the demands of working memory processes.⁵⁻⁶ Based on previous research, the current study will collect ecological momentary assessment (EMA) data for a 1-week baseline period, followed by a 2-week intervention phase in which participants will be randomly assigned to the experimental condition (Tetris) or a control condition (assessment only). During the intervention phase, participants will receive a combination of event- and signal-contingent EMA assessments, and the experimental condition will also receive daily prompts to complete Tetris in-between assessments. EMA will be used to assess alcohol craving and consumption during the baseline and intervention phase and deliver the intervention in real-time.

Specific Aim 1: Evaluate the effects of a brief cognitive interference task on alcohol craving among women who report at risk drinking. Hypothesis: Participants in the experimental group, relative to controls, will evidence significantly lower craving 1) immediately after completing the task, and 2) during the 2-week intervention phase.

Specific Aim 2: Evaluate the effects of a brief cognitive interference task on alcohol consumption, as measured by self-report among women who report at risk drinking. Hypothesis: Participants in the experimental group, relative to controls, will demonstrate significantly lower consumption of alcohol (fewer standard drink units) during the 2-week intervention phase and at 1-month follow-up.

Approach

Participants: Forty women who report at risk drinking will be recruited nationally from online campaigns, the community, and locally from the Women's Health Clinic at the Medical University of South Carolina (MUSC). Many women use obstetricians and gynecologists (OB/GYN) as their primary resource for behavioral health care making OB/GYN health care settings an ideal place to provide accessible interventions for AUD to women.² The inclusion criteria for alcohol consumption will be having a positive score on the AUDIT-C (i.e., a score of 3 or greater) at the time of screening. Additional inclusion criteria include: 1) female, any race or ethnicity; 2) ages 21-65; 3) able to comprehend English to provide informed consent and complete the assessments. Exclusion criteria include: 1) currently engaged in treatment for AUD; 2) current clinically significant bipolar affective disorder, schizophrenia, or psychotic disorder; 3) pregnant; 4) imminently suicidal or homicidal; 5) participants taking medications known to affect alcohol craving or consumption and 6) a score of 10 or higher on the Clinical Institute of Alcohol Withdrawal Revised (CIWA-R).²⁴

Study Procedures

Initial Screening. Potential participants will complete a brief screener over the phone or via REDCap to determine initial eligibility. The brief screener will ask yes/no and multiple choice questions focused on inclusion/exclusion criteria.

Upon enrollment, participants will be given a full description of study procedures and asked to sign an electronic IRB-approved consent form before any additional study procedures or assessments, aside from the initial screener, are conducted. E-consent will be completed on REDCap. Participants will be sent a link to review the e-consent. Research staff will review the consent form over the phone or teleconferencing and answer any questions. Participants will be given as much time as needed to review the consent form. Participants and staff will sign the form electronically. A PDF of the completed consent form will be emailed securely to participants. Participants will complete a baseline assessment, followed by an EMA assessment period, and a post-experiment visit. To decrease risk regarding COVID-19 and increase feasibility, all study procedures will be

conducted with via telemedicine. Vidyo or doxy.me video conferencing will be used. Participants will complete study measures via a REDcap link.

Baseline Visit: The baseline visit will include interview measures that will be completed on doxy.me or vidyo, and self-report surveys completed on REDcap. Self-report measures include items from the DIAMOND¹⁸ screener, the Alcohol Use Disorder Identification Test (AUDIT),⁸ the patient health questionnaire (PHQ-9)¹⁹ and Stages of Change Readiness and Treatment Eagerness Scale (SOCRATES),⁹ Life Experiences Questionnaire²⁰, Posttraumatic Stress Disorder Checklist for DSM-5 (PCL-5)²¹, Drinking Motives Questionnaire²², the Obsessive Compulsive Drinking Scale (OCD)¹², four items assessing COVID-19 related stress, and Short UPPS-P²³. Interview measures include the Time Line Follow [name] (TLFB),⁷ substance use modules of the DIAMOND, Treatment Services Review²⁵, and for participants who screen positive for mood disorders, psychotic disorders, or suicidality will receive the corresponding modules of the DIAMOND. Eligible participants will be instructed on how to complete ecological momentary assessments (EMAs), including instructions on how to measure a standard drink and report craving. Participants will be randomized to the experimental or control condition stratified by self-report craving and depression scores. Participants assigned to the experimental condition will be instructed on how to complete the Tetris task.

[figure not shown]
EMA Assessment Period: The current study will employ a 1-week baseline EMA period followed by a 2-week experimental EMA protocol that uses a combination of event- and signal-contingent assessments. Based on previous EMA research, participants will be instructed to initiate a morning assessment each day to assess behaviors that may not have been captured during the in-vivo assessments the previous evening (*“How many alcohol drinks did you consume yesterday?; How many alcohol drinks do you plan to consume today?”*)¹⁰. They will be provided with examples of standard drinks to help accurately assess their drinking. In addition, participants will complete the imagery subscale from the Craving Experience Questionnaire (CEQ)¹¹ to retrospectively measure their strongest episode of craving during the previous day. Participants will also be prompted once per day to complete a Cue Reactivity Ecological Momentary Assessment (CREMA). CREMA provides real-time responses to alcohol-related stimuli presented in participant’s natural environment. Participants will be randomly prompted between 2:00-9:00 PM to begin a CREMA session. Participants will have 60 minutes to respond to the prompt. Participants will complete baseline measure of craving, stress and mood, and then view a photograph of an alcoholic beverage. Each item will be presented for 30 seconds. Different photographs will be presented at each study trial. After viewing the photograph, participants will be complete post ratings of their craving, stress and mood.

Between the hours of 2:00 p.m. and 9:00 p.m., participants will receive up to three random text message prompts to complete in-vivo assessments assessing craving and mood including: “How many standard drinks have you consumed since your last assessment?; “Are you drinking alcohol right now?; “How is your mood right now?; “How stressed do you feel right now.” “How strong is your craving for alcohol right now...” An automated text message system will be used with at least 1-hour between assessments and will de-activate after an hour has expired. Participants who responded to at least 80% of the morning assessments will be invited to continue participation in the experimental portion of the study.

During, the experimental phase, the same assessments will be administered. In addition, any occasion in which a positive response to current craving is reported, an automated prompt will be displayed to re-rate cravings four minutes later. Participants in the experimental condition will receive an automated prompted to complete the Tetris task in-between the ratings. After four minutes the application will upload a screen shot of the Tetris game into RedCAP. The Tetris task involves manipulating basic shapes to form rows that then disappear. Participants in the experimental condition will be asked to play Tetris after CREMA sessions and after any of the three random craving assessment that participants report experiencing craving. Participants in the control condition will just be asked to re-rate craving four minutes later and report what activities they completed during the three-minute break.

Post-Experiment Assessment: Participants will complete self-report questionnaires via REDCap. In addition, participants will complete the TLFB over a video call at a 1-month follow-up. Figure 1 below illustrates the study design.

Figure 1. Study design

Statistical Analyses

To establish feasibility, descriptive analyses will be used to measure the proportion of prompts participants respond to, and the response time to complete prompts. An intent-to-treat analysis will be conducted with mixed-effects regression to test between-group differences in urge to drink after completing the task, nested within individuals. We will use a random-effects mixed modeling approach using maximum likelihood estimation to test differences in mean craving and drinking outcomes (i.e., alcohol consumption) between baseline and post-experiment. We will test differences in alcohol consumption between baseline and one-month follow-up. Participants will be modeled as random factors and the group allocation will be a fixed factor. Maximum likelihood estimation will provide unbiased estimates assuming missingness at random.¹³

Impediments and Future Directions: While we have chosen a reasonable starting point for alcohol consumption to be eligible for participation, this pilot study will allow us to ascertain this range for alcohol consumption and, if necessary, change the drinking inclusion criterion to more closely match the population motivation and health needs. Future studies can build on this pilot data to further focus the intervention more clearly on the patients of greatest need and who might benefit most from this cognitive interference technique. Also, data collected in this study will provide information on the sustainability of the effect and whether longer intervention periods are necessary or perhaps whether repeat “bolus” interventions might be required. Irrespective of outcome, conducting this research is novel and could lead to stronger collaborations that will ultimately improve the health of women by providing mechanisms to detect and assist in reducing harmful alcohol consumption.

HUMAN SUBJECTS RESEARCH

The proposed research meets criteria for an NIH clinical trial. A Detailed Data and Safety Monitoring Plan is provided. This plan includes continuous, close monitoring by the study investigators and prompt reporting procedures. All procedures and materials will be reviewed and approved by the Institutional Review Board (IRB) at the Medical University of South Carolina (MUSC) before any study procedures occur.

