1. RISKS TO SUBJECTS

[name] and co-investigators on this project have completed the Miami Collaborative IRB Training Initiative (CITI) online training. The candidate is a licensed clinical psychologist (South Carolina #1570). The investigators on the research team includes a licensed clinical psychologist ([name]) and board-certified psychiatrists (Drs. [name] and [name]) with extensive clinical research experience in alcohol use disorder (AUD), randomized clinical trials, and women’s health. All research activity, informed consents and continuing reviews will be reviewed by the MUSC IRB in compliance with 45CFR46 before the research is initiated. Continuing review will occur annually.

Human Subjects Involvement, Characteristics, and Design: A total of 40 women between the ages of 21 and 65 who report at risk drinking will be enrolled over a 1-year period. Participants will be randomly assigned (1:1) to the experimental group or an assessment-only group using a computer-generated randomization scheme ($N=20$) in the experimental condition; $N=20$ in the assessment-only condition). Ecological momentary assessments (EMA) will be used to collect baseline data on craving and alcohol consumption during a 1-week baseline phase. Participants will complete a morning assessment and receive random prompts four times per day during the hours of 2 PM – 9 PM. One of the prompts will be to complete a Cue Reactivity Ecological Momentary Assessment (CREMA). During the 2-week experimental phase, participants will continue to receive EMA prompts. In addition, when participants report alcohol cravings, they will be prompted to re-rate their cravings four minutes later. The experimental group will receive prompts to complete a Tetris task during the four-minute period. Post assessments will be completed via self-report questionnaires, followed by a 1-month follow-up assessment conducted by telephone or video conferencing.

Participants will be recruited nationally from online campaigns and from primary care, and Women’s Health at the Medical University of South Carolina using flyers and physician referral (see

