Recruitment. In order to have 32 participants complete the proposed pilot randomized controlled trial (see power analysis) we will recruit 40 participants to accommodate for expected attrition rates of 20%. Participants will be recruited nationally from online campaigns, the community, and from primary care/Women's Health at the Medical University of South Carolina (see Letter of Support from Vice Chairman of the Department of Obstetrics and Gynecology). IRB approved research staff (e.g., [name], [name], [name]) will also meet with interested patients in a private room within Women's Health to inform them about the research study. Research staff will only meet with potential participants who indicate to someone directly involved in their clinical care (e.g., nursing staff) that they agree to talk with research staff about the study. Research staff will provide a brief overview of the study and those who are interested in learning more will be provided with a link to the online screener. Flyers will be posted throughout Women's Health to recruit potential participants. Prospective subjects will be informed of the study by someone directly involved in their clinical care via a flyer that includes research staff contact information. The candidate has used these methods successfully in the past to recruit subjects for her dissertation research in a fertility and reproductive medicine clinic. In addition, potential participants will be identified through EPIC and contacted by research staff via phone, email, and mail. IRB-approved study flyers and other approved study materials will be placed in prominent locations in MUSC and community-based clinics (e.g., Charleston Center, CDAP, Sleep and Anxiety Clinic) and central hubs (e.g. Coffee shops). All appropriate permissions will be obtained prior to displaying any recruitment materials at community-based clinics and outside of MUSC. In addition, participants from past MUSC research studies who have consented to be contacted for future research studies will be recruited via telephone screening and/or e-mails. These individuals will be referred to us via other MUSC researchers.

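### Randomisation and Tetris instruction are placed before the baseline EMA week and its 80% gate, so randomised women can miss the intervention-phase EMA and at least one arm reports its EMA baseline knowing its allocation

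*Combined protocol and SAP*

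**What the plan says.** Under Study Procedures, the Baseline Visit paragraph covers EMA training and then allocation: "Participants will be randomized to the experimental or control condition stratified by self-report craving and depression scores." The next sentence reads: "Participants assigned to the experimental condition will be instructed on how to complete the Tetris task." The same section puts the baseline assessment ahead of the EMA period. The EMA Assessment Period paragraph opens that period with one baseline week, followed by two experimental weeks, and sets the condition for going on: "Participants who responded to at least 80% of the morning assessments will be invited to continue participation in the experimental portion of the study."

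The opening overview describes the baseline week as "followed by a 2-week intervention phase in which participants will be randomly assigned to the experimental condition (Tetris" or to assessment only). That can be read as later assignment, although it need not conflict. Human Subjects Involvement, Characteristics, and Design says "Participants will be randomly assigned (1:1) to the experimental group or an assessment-only group using a computer-generated randomization scheme", with 20 per arm and no time point. The later Study Procedures text under Risks to Subjects mentions no allocation step. Figure 1 is not available to this review.

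On analysis, the plan says "An intent-to-treat analysis will be conducted with mixed-effects regression" and "Maximum likelihood estimation will provide unbiased estimates assuming missingness at random." On numbers, Recruitment says "we will recruit 40 participants to accommodate for expected attrition rates of 20" per cent, and Statistical Design and Power has all 40 randomised. That section also defines the outcomes: change in craving from baseline to the intervention phase, and change in daily drinks from baseline to the intervention phase and to one month.

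**The concern.** Taken in the order given under Study Procedures, two things follow.

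1. **The gate acts after randomisation.** A randomised woman below 80% is not invited into the experimental portion, so she contributes no intervention-phase EMA. Intent-to-treat would ordinarily cover all 40 randomised. Nothing in the available text says whether these women are asked for post-experiment and 1-month data, whether their baseline-week records stay in the model, or whether they count in the 20% dropout.
2. **The EMA baseline is not blind to arm.** A woman taught Tetris at the baseline visit knows her allocation throughout the baseline week. Nothing in the available text withholds it. Craving and drinks are self-reported, and that week is the reference for the change comparisons.

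At stake are a clear analysis set and an EMA baseline that is comparable between arms by randomisation.

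**Working it through.** **The plan's own number.** Inputs are 32 completers and 20% dropout (Statistical Design and Power). 32 / (1 − 0.20) = 40, as stated. The total allowance for loss is 40 − 32 = 8.

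**The gate in mornings.** 0.80 × 7 = 5.6. Since 5/7 = 71.4% fails and 6/7 = 85.7% passes, a woman needs 6 of 7. The gate sentence does not name the baseline week, but no other mornings precede the experimental portion.

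**Gate loss, illustration only.** The documents give no morning response rate. Assume independent mornings with response probability p. Then P(pass) = 7p⁶(1 − p) + p⁷.
- p = .95: .2573 + .6983 = .956. Expected failures are 40 × (1 − .956) = 1.8, leaving 38.2. The chance that at least one of 40 fails is 1 − .9556⁴⁰ = 84%.
- p = .90: .3720 + .4783 = .850. Expected failures are 40 × (1 − .850) = 6.0, leaving 34.0. The chance that at least one of 40 fails is above 99%.

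If mornings are correlated within a woman (beta-binomial, assumed ICC .1 to .5), expected failures are 3.1 to 3.5 at .95 and 6.3 to 7.2 at .90.

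**Awareness and the group-by-time contrast.** Let B and P be the baseline-week and intervention-phase means that would be reported without awareness, for arms E and C. Let knowing the arm shift E's values by s₀ in the baseline week and by s₁ later. Then:

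(P_E + s₁ − B_E − s₀) − (P_C − B_C) = [(P_E − B_E) − (P_C − B_C)] + (s₁ − s₀).

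The bias is s₁ − s₀. It is zero if the shift is the same in both periods, and −s₀ only if there is no later shift. If controls also know their arm, the same expression applies to the between-arm difference in shifts.

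**Which comparisons are touched.**
- EMA craving and daily drinks, baseline week against intervention phase: yes.
- One-month drinking measured against the daily-report baseline, which Statistical Design and Power allows: yes.
- One-month timeline follow-back (TLFB) against the baseline-visit TLFB: no. That interview belongs to the baseline assessment, before EMA starts.
- The four-minute craving re-rating: no. It does not use the baseline week.

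**The case against.** **The timing is not settled.** The overview can be read as assignment at the intervention phase, and the missing figure may show that. This stands, and it is why reconciliation comes first. But if later assignment was intended, the two sentences in the Baseline Visit paragraph are misplaced and still need correcting.

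**Maximum likelihood covers the gate.** The gate depends only on observed morning response counts. If baseline response is missing at random and these women's baseline-week records stay in the model, the planned analysis handles the resulting missingness. This stands on those conditions, but the plan does not say that the records stay. What remains is lost intervention data and an unclear dropout count.

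**The baseline shift may cancel.** A reader might infer that any awareness shift at baseline passes one for one into the treatment contrast, so that an assumed 0.10 SD would be 0.10/0.50 = 20% of the planned d = .50. The documents do not support that. The experimental arm is prompted to play Tetris throughout the intervention phase, so its later reports are arm-aware too, and only s₁ − s₀ enters. Disclosing after baseline sets s₀ to zero but leaves s₁, so a persistent shift that cancels under the present order would then enter in full. The documents do not show which order biases the contrast more.

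**Gate losses may be small.** A reader might take lower response rates (11.3 failures at .85, 16.9 at .80) and infer that the gate alone exhausts the allowance of 8. Nothing in the documents supports those rates. Retention pays $2 per morning, gives a $10 bonus at six mornings (the same count as the gate) and sends reminders. The higher rates are more plausible.

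**Conclusion.** The point holds as a matter of order and of missing rules, not as a demonstrated bias. Followed as written, Study Procedures places a gate after randomisation and has at least the experimental arm report its EMA baseline knowing its allocation. The text available does not say how randomised women who fail the gate are handled.

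No size of bias can be derived. At the two assumed response rates, expected gate failures are about 2 or 6 of 40. They use part of the allowance of 8 (up to about 7 with the assumed clustering), and other dropout comes on top. Even at .95 at least one failure is likely (84%), so a rule is needed.

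Confidence is medium because the overview permits later assignment and the design figure could not be seen. The case for change rests on a baseline collected before disclosure and an unambiguous analysis set.

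**What to change.** **Preferred.** Amend the opening overview, Baseline Visit, EMA Assessment Period, and Human Subjects Involvement, Characteristics, and Design so that they agree:
- Randomisation, arm disclosure and Tetris instruction take place remotely after the baseline EMA week, only for women who meet the 80% rule, stratified by the craving and depression scores from the baseline visit.
- Intent-to-treat means all women randomised at that point.
- Statistical Design and Power is restated so that 40 is the number starting the baseline week, and gate loss is reported as a feasibility result with those 40 as denominator.

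**Cost.** A short amendment and one brief remote contact per woman at the end of week 1. Randomisation is already computer-generated and the stratifiers are already collected. Fewer than 40 are randomised: about 38 at .95 or 34 at .90, which leaves room for 6 or 2 further losses before falling below 32. Randomising 40 would instead need 40/.956 = 41.9 (42) or 40/.850 = 47.04 (48) starters. The retention precision is kept if the 40 starters are the denominator: 1.96 × √(.8 × .2/40) = 12.4 points, or 13.3 by the exact method, against the stated 13. Among randomised women only, the first formula gives 12.7 (n = 38.2) or 13.4 (n = 34.0).

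**Minimum alternative.** Keep allocation at the visit, but withhold disclosure and Tetris instruction until week 1 ends. Ask all randomised women for post-experiment and 1-month data, keep their baseline EMA in the model, and analyse them as randomised. State whether gate failures count in the 20% dropout. This cures the arm-aware baseline but not the loss of intervention-phase EMA.

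Neither option removes arm-aware reporting during the intervention phase, which belongs to the open design.

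### The protocol conflicts on when Tetris follows a CREMA session and does not fix which occasions are re-rated in each arm

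*Combined protocol and SAP*

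**What the plan says.** The combined protocol and SAP describes the experimental phase in several places.

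- **EMA Assessment Period, re-rating rule.** On "any occasion in which a positive response to current craving is reported, an automated prompt will be displayed to re-rate cravings four minutes later". No arm is named. Participants in the experimental condition "will receive an automated prompted to complete the Tetris task in-between the ratings".
- **EMA Assessment Period, Tetris occasions.** A few sentences later, the experimental arm "will be asked to play Tetris after CREMA sessions and after any of the three random craving assessment"; the sentence then closes with a condition of reported craving.
- **EMA Assessment Period, control arm.** "Participants in the control condition will just be asked to re-rate craving four minutes later and report what activities they completed" "during the three-minute break". This sentence names no trigger and does not mention CREMA.
- **Section 1, Risks to Subjects (design paragraph).** "when participants report alcohol cravings, they will be prompted to re-rate their cravings four minutes later". Tetris is prompted within that four-minute period, and no separate Tetris after CREMA is mentioned.
- **Introduction.** The experimental arm gets Tetris prompts every day between assessments, with no craving condition.

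A CREMA session takes a craving rating before the alcohol photograph and another after it. Statistical Design and Power defines the immediate outcome as a decrease in a single visual analogue craving item straight after the task. The model sentence there speaks only of differences in craving items after the task. Neither it nor the Statistical Analyses section says which occasions are eligible or whether the pre-task rating enters the model.

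**The concern.** The first hypothesis of Aim 1 compares craving between arms immediately after the task. That comparison is fair if both arms are re-rated on the same kind of occasion, after the same interval, from the same starting point. The text leaves all three open for CREMA sessions.

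Take a woman who reports no craving at a CREMA session. On the natural reading of the Tetris-occasions sentence, she plays Tetris if she is in the experimental arm. The re-rating rule gives her no second rating in either arm. Yet Tetris is placed between two ratings and the outcome is taken after the task, so someone programming the app could reasonably add a rating after every game. The experimental arm would then supply craving-free re-ratings that controls might not. Such occasions lower a mean of post-task levels and shrink a mean fall, in both cases without any effect of Tetris.

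**Working it through.** **Number of occasions.** The Retention section gives 56 afternoon and evening prompts over the two weeks. The daily schedule reproduces this: (3 random + 1 CREMA) × 14 days = 56, made up of 42 random prompts and 14 CREMA sessions. The ambiguity concerns at most 14/56 = 25% of occasions, and among those only sessions without reported craving.

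**Assumptions, none given by the documents.** All prompts are answered. Craving is reported on a proportion p of occasions, the same for CREMA and random prompts. Tetris has no effect. The mean re-rating is 40 out of 100 on craving occasions and 0 otherwise. For change scores, craving falls naturally by 10 points on craving occasions and by 0 otherwise.

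**Reading A: re-rating only after reported craving, in both arms.** Each arm has 42p + 14p = 56p re-ratings by the same rule, so nothing is shifted. The experimental arm also plays 14(1 − p) games with no re-rating.

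**Reading B: experimental arm re-rated after every game, controls only after craving.** The experimental arm has 56p + 14(1 − p) = 42p + 14 re-ratings; controls have 56p. The experimental mean level is 40 × 56p/(42p + 14), against 40 in controls. The experimental mean change is −10 × 56p/(42p + 14), against −10.

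| p | Control re-ratings, 56p | Craving-free CREMA games, 14(1 − p) | Experimental re-ratings under B | Mean level under B (control 40) | Mean change under B (control −10) |
|---|---|---|---|---|---|
| 0.25 | 14 | 10.5 | 24.5 | 22.9 | −5.7 |
| 0.50 | 28 | 7 | 35 | 32.0 | −8.0 |
| 0.75 | 42 | 3.5 | 45.5 | 36.9 | −9.2 |

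Under B, levels favour Tetris by 17.1, 8.0 and 3.1 points, and change scores count against it by 4.3, 2.0 and 0.8 points. These are simple means over occasions; a mixed model would weight women somewhat differently.

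**A different craving rate at CREMA.** Let the rate be c at random prompts and k at CREMA. The craving-free share of experimental re-ratings under B is 14(1 − k)/(42c + 14).

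- c = k = 0.40: 8.4/30.8 = 27%.
- c = 0.40, k = 0.60: 5.6/30.8 = 18%.
- Extremes examined: 50% (c = k = 0.20) and 0% (c = 0.80, k = 1).

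If craving-free re-ratings are 0, the experimental mean level is lower by that same percentage.

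**The case against.** A reader might infer that the two arms are re-rated on different occasions, so that the immediate comparison is confounded. The documents do not support that. The craving trigger is stated without limiting it to an arm, in both the EMA section and the human-subjects section, and CREMA sessions include craving ratings. Read literally, the same rule governs re-rating in both arms.

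Two other readings also match the arms. The control sentence directly follows the list of Tetris occasions and may be meant as their counterpart on all of them. The closing craving clause may be meant to cover CREMA as well as the random prompts. Bias from unequal re-rating needs one particular combination, with craving-free re-rating in the experimental arm only, and no section states it.

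The sizes under that combination rest on assumed inputs. More craving at CREMA than at random prompts, which is plausible after an alcohol photograph, makes them smaller. The outcome definition speaks of a decrease, and on that scale the bias is against Tetris. The three-minute figure stands beside four minutes in one sentence and is probably a slip.

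All of this stands, and it rules out asserting confounding as a fact. It does not settle which rule the app follows, what controls do after CREMA, or which CREMA rating counts. The model sentence also leaves levels against change open.

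**Conclusion.** This is an internal inconsistency, with bias as a possible consequence and not an established one. The introduction, the EMA section and the human-subjects section differ on whether Tetris after CREMA depends on reported craving. The control procedure, the interval and the CREMA starting rating are incompletely specified.

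Under a shared craving trigger the re-rating rule is the same in both arms. The cost is then games without an immediate outcome, for example 7 of 14 CREMA games at p = 0.50. A smaller issue remains: those unpaired games could change later craving, and so which later occasions trigger a re-rating, because the trigger is measured after randomisation.

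Under one-sided re-rating, up to 14 of 56 occasions per woman are affected. An unadjusted analysis of levels is then biased towards Tetris and an analysis of change against it. The amounts in the table hold only for the stated assumptions on craving rates, rating values and complete response.

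**What to change.** 1. Reconcile the introduction, the EMA Assessment Period and the human-subjects design paragraph on whether Tetris and re-rating after CREMA depend on reported craving. Which rule to keep is for the investigators; the statistical requirement is symmetry.
2. Whichever rule is kept, state that the re-rating occasions and the interval are identical in both arms, and reconcile the three- and four-minute figures.
3. Name the CREMA craving rating (before or after the photograph) that serves as trigger and as starting value.
4. In Statistical Design and Power, restrict the immediate-craving analysis to occasions re-rated by the same rule in both arms. Include the starting craving rating and occasion type (CREMA or random) in the mixed model.

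The cost is a small change to the app's branching, a short amendment and possibly some extra control re-ratings (at most 14 per woman, one per CREMA session). The starting ratings are already collected. A re-rating that was never requested cannot be recovered later. If the app is already in use, its branching should be documented and item 4 applied to the data as collected.
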